### **5.2.2. Personal/Professional Representative consent**

If a patient is not considered to have capacity to consent, then a Personal Representative or Professional Representative will be approached for consent.

#### **In Scotland this is defined as:**

1. Personal legal representative i.e. Adult's Welfare Guardian or Welfare Attorney, or if not appointed the adult's nearest relative.
2. Professional legal representative i.e. a doctor responsible for the medical treatment of the adult if they are independent of the study, or a person nominated by the healthcare provider.

#### **In England and Wales this is defined as:**

1. Personal legal representative i.e. a person not connected with the conduct of the trial who is suitable to act as the legal representative by virtue of their relationship with the adult and is available and willing to do so.
2. Professional legal representative i.e. a doctor responsible for the medical treatment of the adult if they are independent of the study, or a person nominated by the healthcare provider.

If a Personal Representative is present, they will be given information about the trial in the Personal Representative Information Sheet. The Personal Representative will be given enough time to consider the trial and ask questions regarding their relative's participation in the trial. Ideally, a period of 30-40 minutes will be given but this may be only 10-15 minutes due to the need for fluid resuscitation to begin within one hour.

The Personal Representative will be told they are being asked to give consent on behalf of the incapacitated adult, that they are free to decide whether they wish to make this decision or not and that they are being asked to consider what the adult would want, and to set aside their own personal views when making this decision. They will be informed that their relative will be asked whether or not they wish to continue in the study once they have regained capacity to do so.

If they indicate they have had time to consider the trial, the impact on their relative and provided with the opportunity to have any trial related questions they will be asked to

provide written consent. The Investigator or delegated member of the trial team and the Personal Representative will sign and date the Consent Form to confirm that consent has been obtained. The original consent form will be filed in the Investigator Site File (ISF), the participant will receive a copy of this document and a copy filed in the participant's medical notes.

### **Consent via Telephone**

Every effort will be made to approach and consent the Personal Representative in person. If the Personal Representative is only contactable by telephone then the informed consent process is permitted via telephone or an appropriate video conferencing technology such as NHS near me, provided the following:

- The Representative who is being contacted has previously had the opportunity to discuss the clinical aspects of the patient's care with the clinical team;
- A member of the clinical team has sought permission for the Personal Representative to be contacted by a member of the clinical or research team regarding potential involvement in the study;
- The approach to discuss consent is clearly separate to any discussions made between the representative and the clinical team.

A member of the research team will contact the Personal Representative by telephone/videoconferencing technology to explain what the study entails and answer any questions they may have. The Personal Representative will be given time to read and consider the information sheet. In situations where the Personal Representative does not have a copy of the PIS this will be read to them. Ideally, a period of 30-40 minutes will be given but this may be only 10-15 minutes due to the need for fluid resuscitation to begin within one hour. If the Personal Representative chooses to enrol the patient onto the study, verbal consent will be obtained by a member of the research team who conducted the interview and will sign the consent form. This will be witnessed by an independent member of staff.

A copy of the signed Personal Rep Witness consent form will be sent to the Personal Representative electronically or by post along with a Personal Representative PIS and Consent form for signature by the Personal Representative. All efforts will be made to obtain a signature on the Personal Representative Consent form either electronically or by post. However, in the absence of this signature, a consent form completed by a member of the research team and witnessed by an independent member of staff will be acceptable.

If there is no response from the Personal Representative one further reminder can be sent after one month. If the Personal Representative does not return the signed consent form but does not ask for the participant to be withdrawn from the trial, the Professional Representative consent will remain valid and the patient will remain in the trial.

If a Personal Representative objects to the inclusion of the patient in the trial, their views will be respected.

The participant must also receive information, according to their capacity of understanding, about the trial and its risks and benefits.

If there is not a Personal Representative immediately available (within 30 minutes), a Professional Representative will be approached to determine if it is appropriate for the patient to be entered into the trial so that treatment could be commenced within one hour. A Personal Representative should be approached for consent to continue as soon as they are available, and it is feasible to do so. If the Personal Representative is unable to visit the hospital in person the consent form will be sent to them by post. The Personal Representative will be asked to return the signed consent form if they wish to remain in the trial, or contact the study team if they wish to be withdrawn. If the patient does not return the signed consent form but does not ask to be withdrawn from the trial, the Professional Representative consent will remain valid.

### **5.2.3. Deferred Consent**

Patients who have “life threatening features” and who lack temporary capacity due to their current illness can be recruited to the trial using deferred consent if there is no Personal/Professional Representative to give consent on their behalf within 30 minutes so that treatment can be commenced within one hour. The decision to defer consent should be made by an ST4 (or above) or consultant who has appropriate trial training and this should be clearly documented.

The patient would be enrolled into the trial and receive their allocated treatment. Consent would be sought as soon as possible from a Personal Representative (or a Professional Representative if they are available sooner). If a Personal/Professional Representative declines to give consent for continuation at this stage, their wishes will be respected and the withdrawal process in section 5.6 will be followed.

### **5.2.4. When the participant regains capacity**

If and when the participant regains capacity to consent (as assessed by a clinician), they will be given a Recovered Capacity PIS which will explain what has happened to them so far and seek written consent for continued participation in the trial. This will be done as soon as it is feasibly possible. If the participant is happy to continue they will be asked to provide written consent. The Investigator or delegated member of the trial team and the participant will sign and date the Consent Form to confirm that consent has been obtained. The original consent form will be filed in the Investigator Site File (ISF), the participant will receive a copy of this document and a copy filed in the participant’s medical notes.

In the event that a patient is not able to be approached for consent to remain in the trial prior to hospital discharge, the local research team will seek written consent by sending a PIS and consent form by post. The patient will be asked to return the signed consent form if they wish to remain in the trial, or contact the study team if they wish to be withdrawn. If there is no response, one further reminder can be send after one month by post. If the patient does not return the signed consent form but

does not ask to be withdrawn from the trial, the Professional Representative and/or Personal Representative consent will remain valid and the patient will remain in the trial.

If the participant is not happy to continue, the withdrawal process in section 5.6 will be followed.

[figure not shown]
For any patient who was included but does not regain full capacity, consent from the Personal Representative will stand, or from the Professional Representative where there is no Personal Representative. Where no consent is given by any legal representative, i.e. deferred consent is used and no subsequent consent obtained, or a participant dies before any consent obtained the patient data collected would be destroyed.

Patients with permanent incapacity will not be recruited and this is an exclusion criteria.

#### **5.2.5. Witnessed Methods of Obtaining Signatures**

Consent will normally be recorded in writing, dated and signed or otherwise marked by the participant or their legal representative. In most instances this will take the form of a face to face consent process with a wet ink signature.

If face to face consent is not possible or feasible, verbal consent over the phone or video-call will be utilised, this will be witnessed and recorded in writing. If a verbal witnessed consent procedure is utilised we will also attempt to obtain a written signature from the participant or their legal representative by posting the consent form to them for signature and return.

### **5.3 SCREENING FOR ELIGIBILITY**

Participant eligibility will be verified by a clinical trial physician. Confirmation of eligibility will be recorded on the eligibility form/eCRF and within the participants' medical records.

### **5.4 INELIGIBLE AND NON-RECRUITED PARTICIPANTS**

Patients who are eligible for inclusion but are not recruited will be recorded on the screening log to provide data to comply with CONSORT reporting for randomised controlled trials. The Data Protection Act will be complied with at all times.

### **5.5 RANDOMISATION**

#### **5.5.1 Randomisation Procedures**

After assessment for eligibility and consent, the researcher or a delegated member of the clinical team will collect the baseline data necessary to complete the pre-randomisation information on the eCRF (a blood lactate measurement is required in order to complete the randomisation). Vital signs and blood lactate taken within the last hour can be used to make the assessment. Use of clinical care results taken prior to consent is permitted. If greater than one hour ago, a further blood lactate should be measured prior to randomisation. Randomisation will be carried out using a web-based randomisation service (managed by the Edinburgh Clinical Trials Unit (ECTU)) that ensures allocation concealment. Randomisation will be carried out within 12 hours of arrival at the hospital and within one hour of the decision being made that fluid resuscitation should be commenced. Once a patient is randomised, they will remain in the study and have all outcomes recorded regardless of compliance with randomised pathway allocation, unless they specifically withdraw consent to have data stored. Consented patients will be randomised on a 1:1 basis to albumin or balanced crystalloid in addition to standard care and will be stratified by age (<70 and ≥70) and lactate (<2 and ≥2) and study site.

#### **5.5.2 Treatment Allocation**

5% Human Albumin Solution will be compared to balanced crystalloid. This is an open label study.

##### **1. 5% Human Albumin Solution arm**

Participants will receive 5% albumin as their sole resuscitation fluid in the first six hours following recruitment to the study. See section 6.3 for dosing and 6.5 for overdose. All other care will be as per local protocol.

##### **2. Balanced crystalloid arm**

Participants will receive balanced crystalloid as their sole resuscitation fluid in the first six hours following recruitment to the study. All other care will be as per local protocol.

#### **5.5.3 Emergency Unblinding Procedures**

The study will be not be blinded, treating clinicians will be aware of which treatment the participant is receiving.

## **5.6 WITHDRAWAL OF STUDY PARTICIPANTS**

Participants are free to withdraw from the study at any point or a participant can be withdrawn by the Investigator or their Personal/Professional Representative. If withdrawal occurs, the primary reason for withdrawal will be documented in the participant's eCRF, if possible. The participant/their Representative will have the option of withdrawal from:

1. Study treatment with continuation of the collection of clinical and safety data;
2. All aspects of the trial but continued use of data collected up to that point. To safeguard rights, the minimum personal information possible will be collected.

Randomised patients who wish to be withdrawn from the study before they have undertaken any study related procedures will be withdrawn from the study and another participant will be recruited to replace them. Data on the original participant will be kept on the eCRF/database.

We anticipate ~1% withdrawal as previously found in the 3CPO, RATPAC and RAPID-CTCA trials [38-40].

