## 3 Overall Statistical Principles

The intention-to-treat (ITT) population will include all patients who have been randomised into this trial, and who did not withdraw consent for any of their data to be stored in the trial database. Patients will be analysed in the group to which they were allocated, regardless of the

intervention they actually received. Analyses will be based on the ITT population, unless otherwise specified; in addition, we will explore the influence of adherence on the range of treatment estimates using a suitably specified per-protocol approach (see Section 4.6, analysis (a)).

Safety data will in the first instance be analysed according to treatment received, and will also be summarised descriptively according to an intention to treat approach.

In general terms, categorical data will be presented using counts and percentages, whilst continuous variables will be presented using the mean, median, standard deviation (SD), minimum, maximum, lower and upper quartiles and number of patients with an observation (N). Data will be split by intervention group and time point where applicable.

All applicable statistical tests will be 2-sided and will be performed using a 5% significance level – but all such tests of hypothesis will be informal and interpreted descriptively. 95% (2-sided) confidence intervals (CIs) will be presented.

Where there is missing data for an outcome variable, in the first instance, those records will be removed from any statistical analysis relating to that outcome variable (complete case analysis), unless otherwise specified. In tabulations, numbers of missing observations will be provided, but percentages will not include them.

Distributional assumptions underlying the statistical analyses may be assessed by visual inspection of residual plots. Normality may be examined by normal probability plots. If the distributional assumptions for the parametric approach are not satisfied, further data transformation (to alleviate substantial skewness (i.e. normalizing) or to stabilise the variance), or other suitable methods will be considered. This will be documented in the statistical results report together with the reasoning supporting the action taken, if applicable.

Sites may be categorised into small sites (less than 10 participants recruited) versus big sites (10 or more participants recruited).

All analysis and data manipulation will be carried out using SAS [1] unless otherwise stated.

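### Protocol 5.6 conflicts with 5.5.1 on whether outcomes are still collected after withdrawal, so 30-day mortality status can be lost in an arm-dependent way in an open-label trial

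*Protocol*

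**What the plan says.** Protocol 5.5.1 gives the retention rule: "Once a patient is randomised, they will remain in the study and have all outcomes recorded regardless of compliance with randomised pathway allocation". It has one exception: "unless they specifically withdraw consent to have data stored".

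Protocol 5.6 has three provisions that bear on this.

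- Replacement. Some participants "will be withdrawn from the study and another participant will be recruited to replace them". The group that this covers is described as "Randomised patients who wish to be withdrawn from the study before they have undertaken any study related procedures". On what has already been recorded, the section adds: "Data on the original participant will be kept on the eCRF/database".
- Who may withdraw someone. Besides the participant's own choice, "a participant can be withdrawn by the Investigator or their Personal/Professional Representative". No criteria are given for the investigator.
- What withdrawal covers. The participant or representative may choose between stopping study treatment with data collection continuing, and leaving "All aspects of the trial but continued use of data collected up to that point". This choice is not extended to withdrawal by the investigator.

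Protocol section 9 says that, when consent is withdrawn or refused, data up to that point enter the intention-to-treat analysis. Section 3 takes the 30- and 90-day follow-up from routine data alone. Sections 5.1 and 5.5.3 make the allocation known once randomisation is done.

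SAP section 3 defines the intention-to-treat population as "all patients who have been randomised into this trial, and who did not withdraw consent for any of their data to be stored", and removes records with a missing outcome from the analysis of that outcome. SAP section 4 has no rule for replaced patients and no missing-outcome sensitivity analysis for mortality.

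**The concern.** A site cannot follow both sections as written. The replaced patient's data are kept, so consent to storage has not been withdrawn. Section 5.5.1 then requires that patient to stay in with all outcomes recorded, while 5.6 takes the patient out of the study, which is more than taking them off treatment.

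The decision to leave, or to withdraw someone, is made when the arm is known. If the reasons for leaving differ between albumin and crystalloid, and leaving ends follow-up, the patients whose 30-day status is missing will differ between arms. A complete-case analysis then compares groups that are no longer exactly those randomised. The mortality estimate and its interval are meant to inform a definitive trial, and the same withdrawal rule could be carried into it.

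The loss is also avoidable. Day 30 and Day 90 status need no visit and nothing further from the patient.

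**Working it through.** **1. The rules side by side**

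| Situation | Protocol 5.5.1 | Protocol 5.6 |
|---|---|---|
| Asks to leave before any study procedure, data kept | Stays in, all outcomes recorded | Withdrawn from the study and replaced |
| Withdrawn by the investigator | Stays in, all outcomes recorded | Withdrawn; continued follow-up not stated |
| Refuses storage of data | Excepted | Not addressed |

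The first row is a direct conflict. The second is a conflict or a gap, depending on what withdrawal by the investigator is taken to mean.

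**2. How an outcome becomes missing**

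Leaving all aspects of the trial stops new data (5.6, section 9). The patient remains in the SAP's intention-to-treat population by definition, but has no 30-day status. The complete-case rule then removes the record from the mortality model. Recruiting someone else does not restore the missing value.

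**3. The plan's own power figure (Protocol 10.1)**

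Inputs: 35% against 18%, 300 randomised 1:1 (150 per arm), two-sided 5%. The mean risk is (0.35 + 0.18)/2 = 0.265.

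- SE under no difference: √(2 × 0.265 × 0.735 / 150) = 0.0510.
- SE under the alternative: √((0.35 × 0.65 + 0.18 × 0.82) / 150) = 0.0500.
- z = (0.17 - 1.96 × 0.0510) / 0.0500 = 1.40, so power is 92.0%. This agrees with the stated 90%.

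With 1% lost and not replaced (148.5 per arm) the same formula gives 91.7%. Replacement therefore recovers about 0.3 points of power. Power is 90.6% at 5% loss and 89.0% at 10%.

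**4. Possible shift in the mortality difference**

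Assume no true effect and risk p in both arms. Let k patients be lost from one arm of 150, with death risk q among those lost. The observed risk in that arm is (150p - kq)/(150 - k).

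Protocol 5.6 anticipates about 1% withdrawal: 0.01 × 300 = 3. Take the extreme case in which all 3 come from one arm.

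- p = 35%, all 3 would have died: (52.5 - 3)/147 = 33.7%, a shift of -1.3 points (odds ratio 0.94).
- p = 35%, all 3 would have survived: 52.5/147 = 35.7%, a shift of +0.7 points (odds ratio 1.03).
- p = 20%: 27/147 = 18.4% to 30/147 = 20.4%, shifts of -1.6 to +0.4 points. The 20% is the index-hospitalisation mortality in Protocol 1.1, used as an assumed lower value.

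If withdrawal were 5% of 300 (15 patients), all from one arm, the range at p = 35% would be 37.5/135 = 27.8% to 52.5/135 = 38.9%, shifts of -7.2 to +3.9 points (odds ratio 0.71 to 1.18).

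**5. Yardstick**

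The 95% half-width for the difference with 35% in both arms is 1.96 × √(2 × 0.35 × 0.65 / 150) = 10.8 points.

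**The case against.** The strongest reply is that nothing in 5.6 says follow-up stops for a replaced patient. A withdrawing participant can choose the treatment-only option, 5.5.1 still demands all outcomes, the data are kept, and the SAP retains the patient in the analysis population. That is fair. Stopped follow-up is an inference from the words withdrawn from the study read with section 9. But a site could reasonably read them that way, and for withdrawal by the investigator the documents give no answer. Section 9 does continue adverse event collection after withdrawal, but 11.2 ends that at 7 days, so it does not secure 30-day status.

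It also stands that the replacement window is short, since fluid is to start within about an hour, and that refusals after deferred consent generally come after allocated treatment has begun. Those are withdrawals under 5.6 but not replacements. The investigator's power to withdraw is a separate sentence and carries no right to replace. Analyses are exploratory, and SAP 4.6(d) reports missing-data patterns by arm.

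Three stronger readings are tempting, and the documents do not support them.

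- That replacement itself undoes randomisation. Nothing says that the new participant inherits the vacated allocation. Entry is by concealed web randomisation, and a newly randomised patient does not bias the comparison.
- That an undelivered allocation counts twice as a recruitment success. SAP 4.4 divides the number randomised by the number screened. The replacement is screened too, so both people enter numerator and denominator, and both were in fact randomised.
- That the number randomised could pass 300 without explanation. The replacement rule in 5.6 is the explanation.

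**Conclusion.** The conflict between 5.5.1 and 5.6 is real and should be resolved. It leaves open a route by which 30-day mortality status is lost after the arm is known, and the SAP as written would drop those patients from the mortality model. The documents show that this is permitted, not that it happened.

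At the protocol's own 1% the consequence is small: at most -1.3 to +0.7 points at 35% mortality, or -1.6 to +0.4 at 20%, well inside a half-width of 10.8 points at 35%. It becomes material only if withdrawal is several times higher and falls largely on one arm. These figures are unadjusted. They assume no true effect, all losses in one arm, and the extremes of death risk among those lost; the documents give no arm-specific withdrawal rates.

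The point merits a change because the fix costs little and protects the mortality comparison.

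**What to change.** - Reconcile 5.5.1 and 5.6: declining or stopping trial fluid, including withdrawal by the investigator, does not end outcome collection. This sets no rule on when treatment should stop.
- Collect 30- and 90-day vital status from routine records for everyone randomised, unless the participant or representative has been asked and refuses.
- State in 5.6 and SAP section 3 that a replaced patient stays in the intention-to-treat population and that a replacement is a new, independent randomisation. Alternatively, delete the replacement sentence.
- In SAP 4.1, report withdrawals and replacements by arm, with who initiated each. In 4.6, add a best- and worst-case analysis by arm for missing 30-day status.

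The cost is protocol wording, a line on the withdrawal form and one small sensitivity table. If replacement is dropped, the analysable number may fall slightly below 300, at a cost of about 0.3 points of power at 1% loss. The SAP abstract describes recruitment in the past tense. If recruitment is complete, the SAP changes can still be made, and vital status can still be sought where consent allows.
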